To determine the safety and tolerability of DRF administered for up to 48 weeks in adult East Asian participants with RMS	
 • Incidence of AEs and SAEs up to Week 48 • Quantitative and qualitative changes from Baseline Visit (Day 1) to Week 48 in clinical laboratory parameters, ECGs, and vital signs • Incidence of C-SSRS events at Baseline Visit (Day 1) and through Week 48

Exploratory objectives and endpoints are listed in Section 4.

CONFIDENTIAL

The information contained herein may not be used, disclosed, or published without the written consent of Biogen MA Inc.

Study Design:

This is a multicenter, open-label, single-arm, Phase 3 study to evaluate the safety and tolerability, and PK of DRF administered orally to East Asian participants with RMS. This study will be conducted in 2 parts:

Part 1 is designed to evaluate the PK, safety, and tolerability of DRF administered orally.

Part 2 is designed as a 24-week safety extension period for participants from Part 1.

Study Location:

Approximately 45 sites from Japan and China are planned.

Study Population:

This study will be conducted in male and female participants who meet the following criteria:

- aged 18 to 65 years at the time of informed consent
 - For participants in Japan aged < 20 years, written informed consent should be obtained from the participant and their legally acceptable representative.
 - Informed consent from a legally acceptable representative is not mandatory if the participant is classified as an adult based on the latest applicable local laws.
- diagnosed with RMS according to study eligibility criteria

Detailed criteria are described in Section 6.

Number of Planned Participants:

Approximately 50 Japanese participants and 50 Chinese participants are planned to be enrolled. The Sponsor may enroll fewer than 50 participants per cohort based on the observed recruitment rate in these regions.

Treatment Groups:

The study will consist of 2 treatment cohorts as follows:

- Cohort 1: approximately 50 Japanese participants with RMS

CONFIDENTIAL

The information contained herein may not be used, disclosed, or published without the written consent of Biogen MA Inc.

- Cohort 2: approximately 50 Chinese participants with RMS

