- k. Eligibility related to prior treatment with an investigational drug and/or a commercially available drug for the treatment of MS not listed above within the past 2 years will be determined on a case-by-case basis by the Medical Monitor
- l. Steroids, with the exception of topical or inhaled steroids within 30 days prior to Baseline Visit (Day 1)

Laboratory Values

- 28. Clinically significant abnormal laboratory test values (those that may confound study results or pose risk to the subject through participation in the study), as determined by the Investigator, at Screening or Baseline Visit (Day 1).
- 29. Has any of the following abnormal blood tests at Screening:
 - a. ALT, AST, or GGT $\geq 3 \times \text{ULN}$ or bilirubin $> 2 \times \text{ULN}$.
 - b. TSH level $> 10\%$ of the ULN
 - c. eGFR $\leq 60 \text{ mL/min}/1.73 \text{ m}^2$ (using the Chronic Kidney Disease Epidemiology Collaboration equation) [[Levey 2009](#)]
 - d. Lymphocyte count $< \text{LLN}$
- 30. Has any of the following abnormal urine tests at Screening:
 - a. Beta-2 microglobulin $> 0.3 \mu\text{g/mL}$
 - b. Albumin to creatinine ratio $> 22.6 \text{ mg}/\text{mmol}$

For the parameters listed in Exclusion Criteria 29d and 30, out-of-range values that are clinically not significant, as determined by the Investigator, may be repeated once, and the participant may be enrolled only if the repeated value is within the normal range.

CONFIDENTIAL

The information contained herein may not be used, disclosed, or published without the written consent of Biogen MA Inc.

Other

31. Blood donation (1 unit or more) within 90 days prior to Screening, plasma donation within 1 week prior to Screening, and platelet donation within 6 weeks prior to Screening.
32. History of alcohol or substance abuse within the past year (as determined by the Investigator).
33. Participants who are pregnant or currently breastfeeding and those intending to become pregnant or begin breastfeeding at any point during the study and for 30 days after completing study treatment.
34. Current or prior participation in a clinical trial within 90 days of Screening. Participants who have previously participated in a clinical trial but have not received any IMP treatment within 90 days of Screening will be eligible if the Investigator confirms that the participant meets all other Inclusion and Exclusion criteria and there are no other safety concerns.

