6.3.2. Retesting

For the parameters listed in exclusion criteria 29d and 30, out-of-range values that are not clinically significant, as determined by the Investigator, may be repeated once, and the participant may be enrolled only if the repeated value is within the normal range.

Participants who have abnormal laboratory test values as described in exclusion criteria 29a, 29b, and 29c should not be retested.

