14.2.4. Central Laboratories for Laboratory Assessments

Central laboratories have been selected by the Sponsor to analyze the hematology, blood chemistry, and urine samples collected for this study. PK samples will be analyzed at a laboratory selected by the Sponsor.

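### Exclusion criterion 29b sets the TSH limit at one tenth of the ULN as written, contradicts its own lead-in, and is clarified nowhere else

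*Protocol*

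**What the plan says.** Protocol Section 6.2, Laboratory Values, introduces criterion 29 with "Has any of the following abnormal blood tests at Screening". Item 29b under it reads "TSH level $> 10\%$ of the ULN". The other items are stated differently: 29a uses multiples of ULN, 29c an absolute eGFR, and 29d the LLN.

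Section 6.3.2 (Retesting) says: "Participants who have abnormal laboratory test values as described in exclusion criteria 29a, 29b, and 29c should not be retested". One repeat is open only to other tests: "For the parameters listed in exclusion criteria 29d and 30, out-of-range values that are not clinically significant" may be repeated once.

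TSH is measured only at Screening (Table 1; Table 5, footnote 3). Table 5 lists it under biochemistry, and Section 14.2.4 says: "Central laboratories have been selected by the Sponsor to analyze the hematology, blood chemistry, and urine samples collected for this study". That section gives no TSH limit or range. SAP Table 3, which sets the laboratory thresholds for analysis, has no TSH entry.

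**The concern.** A percentage of the ULN is a fraction of it. Ten percent of the ULN is 0.1 x ULN, so the sentence as printed excludes candidates whose TSH is well inside the normal range. That cannot be squared with a lead-in about abnormal results.

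This is an operative eligibility rule. If a site follows it, suitable candidates are lost from a study with a small target: "Approximately 50 Japanese participants and 50 Chinese participants are planned to be enrolled", and the sponsor may enrol fewer if recruitment is slow (Section 12.7). If sites do not follow it, eligibility rests on a limit that is written nowhere in the two documents. An auditor then cannot verify 29b against the protocol, and the number of eligibility deviations reported under SAP Section 5.4 depends on an unwritten interpretation.

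**Working it through.** The plan states no figure for this criterion, so there is none to reproduce. The check has two parts.

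**1. The text**

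- Literal limit: 10% of ULN = 0.10 x ULN.
- On the scale from zero to ULN, the share of the scale above the limit is (1 - 0.10)/1 = 90%, whatever the ULN is. This is a share of the scale, not of people.
- If the LLN is above 0.10 x ULN, the whole normal range lies above the limit.
- The summary of changes for the current version reprints criterion 29 with the same TSH wording, so an error in reading the PDF is unlikely.
- Criteria 14 and 28 let the investigator exclude for clinically significant abnormalities. They add exclusions and do not override 29b.
- The rescreening routes in criteria 15, 16 and 22 and in Section 6.3.3 concern infection, contact with infection, or a public health emergency. None covers TSH.

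**2. The size, under a stated assumption**

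The documents give no TSH range. Assume that the central 95% of TSH values in people with normal thyroid function runs from LLN to ULN. Write r = LLN/ULN, vary r from 0.04 to 0.15, and set ULN = 1.

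Lognormal shape: mean of log TSH m = ln(r)/2; SD s = -ln(r)/(2 x 1.96). The share above a limit t is 1 - Phi((ln t - m)/s).

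- r = 0.04, t = 0.1: m = -1.609, s = 0.821, z = (-2.303 + 1.609)/0.821 = -0.84, share = 80.1%.
- r = 0.15, t = 0.1: m = -0.949, s = 0.484, z = (-2.303 + 0.949)/0.484 = -2.80, share = 99.7%.
- r = 0.04, t = 1.1: z = (0.095 + 1.609)/0.821 = 2.08, share = 1.9%.
- r = 0.15, t = 1.1: z = (0.095 + 0.949)/0.484 = 2.16, share = 1.6%.

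Normal shape: mean (1 + r)/2, SD (1 - r)/(2 x 1.96), with the same limit t = 0.1.

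| r = LLN/ULN | Above 0.1 x ULN, lognormal | Above 0.1 x ULN, normal | Above 1.1 x ULN, lognormal |
|---|---|---|---|
| 0.04 | 80.1% | 95.7% | 1.9% |
| 0.06 | 89.4% | 96.4% | 1.8% |
| 0.08 | 94.7% | 97.0% | 1.8% |
| 0.10 | 97.5% | 97.5% | 1.7% |
| 0.15 | 99.7% | 98.6% | 1.6% |

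If sites in practice enrol anyone up to 1.1 x ULN, the share of those enrolled who breach the literal text at r = 0.04 is (80.1 - 1.9)/(100 - 1.9) = 79.7%. At r = 0.15 it is (99.7 - 1.6)/(100 - 1.6) = 99.7%. Per 100 such participants, that is roughly 80 to nearly 100 technical breaches.

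**The case against.** The strongest reply is that nobody would apply the literal limit. The lead-in speaks of abnormal tests, a sponsor-selected central laboratory reports the result, and sites have a Medical Monitor and a Study Reference Guide. A limit of more than 10% above ULN fits both the percentage and the lead-in. This stands as a forecast of what sites do, and for that reason near-total screen failure should not be presented as the expected outcome. It does not repair the text, because no passage confirms that reading.

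A reader might infer more, and three such inferences are not supported:

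- **A 100-fold uncertainty.** This takes 10 x ULN as one reading and 0.1 x ULN as the other. Nothing in the text supports turning a percentage into a tenfold multiple.
- **Different populations in Japan and China, or each site guessing alone.** No passage shows that sites or countries read 29b differently, and the study reference guide and laboratory manual are not available to us.
- **Damage to the safety analysis.** The Safety Analysis Set is every dosed participant (Protocol Section 12.2; SAP Section 3.5), so a 29b breach removes no one. Whether it would count as a major deviation depends on the deviations management plan, which we do not have.

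It is also fair to say that the retest bar adds little. It covers 29a, 29b and 29c alike, and a mid-normal TSH repeated against the literal limit would normally fail again. It matters only in that the protocol offers no second look at a 29b result.

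**Conclusion.** The point holds. Criterion 29b is wrong as written: its literal limit conflicts with its own lead-in, and neither document states the intended one. The textual conflict needs no assumption.

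The size does. For LLN/ULN of 0.04 to 0.15, the literal rule would exclude about 80% to over 99% of candidates with normal thyroid function, against about 2% if the limit is 10% above ULN. The lower end comes from the lognormal shape with a low LLN; the normal shape gives about 96% to 99%. A claim that almost every such candidate is excluded therefore goes beyond what can be shown across this range; the large majority is the safe statement.

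The practical consequence is a gap between the written and the applied rule, with technical breaches of 29b in most enrolled participants. No sample-size, precision or analysis-set figure is affected.

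**What to change.** The sponsor should restate 29b as the limit it intends, either as an explicit multiple of the central-laboratory ULN or as an absolute value. It should make the result consistent with the abnormal-test lead-in and with the retest rule in Section 6.3.2. This review does not propose the limit.

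Sites should be told of the correction. TSH values already recorded at Screening, for both screen failures and enrolled participants, should be checked against the corrected limit. SAP Section 5.2 already plans a listing of screening laboratory assessments, which can support that check.

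The cost is one amended line, a notice to sites and a short review of existing Screening data.

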6.3. Screening, Retesting, and Screen Failures

6.3.1. Screening

Once informed consent is obtained, screening assessments can occur. At this time, a unique identification number is assigned that will be used on study-related documents pertaining to the participant. Any identification numbers that are assigned will not be reused, even if the participant does not receive treatment or continue in the study. Study sites are required to document all screened participants initially considered for inclusion in the study.

The screening period can be extended up to a maximum of 42 days (i.e., an additional 2 weeks) with prior approval of the medical monitor if the testing of teriflunomide levels or confirmation of accelerated elimination (per exclusion criterion 27e; Section 6.2) or minimum of 4 weeks' TB prophylaxis (per exclusion criterion 21c; Section 6.2) cannot be completed within the 28-day screening period.

CONFIDENTIAL

The information contained herein may not be used, disclosed, or published without the written consent of Biogen MA Inc.

6.3.2. Retesting

For the parameters listed in exclusion criteria 29d and 30, out-of-range values that are not clinically significant, as determined by the Investigator, may be repeated once, and the participant may be enrolled only if the repeated value is within the normal range.

Participants who have abnormal laboratory test values as described in exclusion criteria 29a, 29b, and 29c should not be retested.

6.3.3. Screen Failures

Screen failures are defined as participants who sign the ICF but are not subsequently dosed. If a participant is considered a screen failure, the reasons for exclusion must be documented in the participant's source documents and on the screening log. A minimal set of screen failure information is required to ensure transparent reporting of screen failure participants to meet the Consolidated Standards of Reporting Trials publishing requirements and to respond to queries from regulatory authorities. Minimal information includes demography, screen failure details, eligibility criteria, and any SAEs.

All participants with incomplete enrollment due to a public health emergency (e.g., travel restrictions, participants who recovered after getting infected) will be eligible for rescreening provided that the participants met all eligibility criteria during the initial screening period, and that the reason for rescreening is incomplete enrollment due to a public health emergency. These participants will be reported as screen failed and then rescreened. Participants may have been provided with a unique identification number during Screening. The previously issued unique identification number will no longer be used, and a separate unique identification number will be provided during rescreening.

CONFIDENTIAL

The information contained herein may not be used, disclosed, or published without the written consent of
Biogen MA Inc.

7. STUDY TREATMENT

7.1. Regimen

Refer to and follow the DHA.

Participants will initiate treatment with DRF 231 mg twice daily on Day 1 through Day 7, followed by 462 mg twice daily from Day 8 onwards, with allowable dose reduction for tolerability from Day 8 onwards. Study staff will administer the first dose of DRF at the Baseline Visit (Day 1).

If a participant misses a dose, doses should not be doubled up to make up for the missed dose. The participant may take the missed dose only if they leave 6 hours between doses. If the participant does not remember to take the dose within 6 hours, this dose should be skipped, and the next dose should be taken as scheduled.

7.2. Modification of Dose and/or Treatment Schedule

Starting on Day 8 of treatment, dose reduction to DRF 231 mg twice daily is permitted at the Investigator's discretion for participants who are unable to tolerate DRF 462 mg twice daily due to flushing or GI disturbances. Once a participant has stabilized after dose reduction, attempts should again be made to achieve and maintain the target maintenance dose of DRF 462 mg twice daily. If a participant remains unable to tolerate DRF 462 mg twice daily after 1 month on treatment, further dose reduction will not be permitted, and the participant will be discontinued from the study.

[REDACTED]

[REDACTED]

[REDACTED]

[REDACTED]

[REDACTED]

CONFIDENTIAL

The information contained herein may not be used, disclosed, or published without the written consent of
Biogen MA Inc.

CONFIDENTIAL

The information contained herein may not be used, disclosed, or published without the written consent of Biogen MA Inc.

7.3. Study Treatment Management

Study treatment will be manufactured, handled, and stored in accordance with applicable Good Manufacturing Practice.

Site staff should follow the DHA for specific instructions on the handling, preparation, administration, and disposal of the study treatment. The DHA aligns with all other references, including the protocol.

Study treatment must be dispensed only by a pharmacist or appropriately qualified staff. Study treatment is to be dispensed only to participants enrolled in this study. Once study treatment is prepared for a participant, it can be administered only to that participant.

7.3.1. DRF

DRF is formulated as enteric-coated minitablets in HPMC capsules for oral administration. Each capsule consists of [REDACTED] minitablets and contains 231 mg DRF. DRF is a white to off-white powder.

DRF delayed-release capsules are supplied in 120-count, 200 cc HDPE bottle configuration.

The contents of the DRF label will be in accordance with all applicable regulatory requirements. At a minimum, the label will include a study reference code, study treatment identifier, quantity of dosage units, lot number, and other pertinent information in accordance with local law. The expiry or use-by date is stored in the IRT system, and printable assignment reports are available to site staff. Study treatment should not be used after the expiry or use-by date.

7.3.1.1. Preparation

The individual preparing DRF should carefully review the instructions provided in the DHA.

If the packaging is damaged, or if there is anything unusual about the appearance or attributes of the bottles or the capsules, do not use the capsules. The bottle in question should be saved at the study site and the problem immediately reported to the Sponsor.

Contact information for reporting a problem is provided in the Study Reference Guide.

CONFIDENTIAL

The information contained herein may not be used, disclosed, or published without the written consent of Biogen MA Inc.

7.3.1.2. Storage

DRF is to be stored at room temperature (not to exceed 25°C) in a monitored and locked cabinet, with limited access. For the most up-to-date storage requirements, follow the instructions provided in the DHA.

7.3.1.3. Handling and Disposal

The Investigator must return all used and unused bottles of DRF as instructed by the Sponsor unless approved for onsite destruction.

If any DRF supplies are to be destroyed at the study site, the institution or appropriate site staff must obtain prior approval from the Sponsor, by providing, in writing, the destruction policy or details of the method of destruction. After such destruction, the Sponsor must be notified, in writing, of the details of the study treatment destroyed (e.g., lot or kit numbers, quantities), the date of destruction, and proof of destruction.

7.3.1.4. Accountability

Accountability for study treatment is the responsibility of the Investigator. The study site must maintain accurate records demonstrating dates and amount of study treatment received, to whom dispensed, amount returned by the participant, and accounts of any study treatment accidentally or deliberately destroyed or lost.

Unless otherwise notified, all bottles both used and unused, must be saved for study treatment accountability. By the end of the study, reconciliation must be made among the amount of DRF supplied, dispensed, and subsequently destroyed, lost, or returned to the Sponsor. A written explanation must be provided for any discrepancies.

7.4. Blinding Procedures

This is an open-label study.

7.5. Precautions

Medications for the treatment of severe hypersensitivity reactions (e.g., epinephrine for SC injections, diphenhydramine for injection) must be available for immediate use.

See the DHA for detailed instructions.

7.6. Compliance

Compliance with treatment dosing is to be monitored and recorded by site staff.

CONFIDENTIAL

The information contained herein may not be used, disclosed, or published without the written consent of
Biogen MA Inc.

7.7. Concomitant Therapy and Procedures

7.7.1. Concomitant Therapy

A concomitant therapy is any drug or substance administered between the participant's Baseline Visit (Day 1) and last study visit.

7.7.1.1. Allowed Concomitant Therapy

Participants should be instructed to contact their Investigators before taking any new medications, including nonprescription drugs and herbal preparations.

Symptomatic therapy such as treatment for spasticity, depression, or fatigue is not restricted but should be optimized as early as possible during screening to maintain consistent treatment for the duration of the study.

7.7.1.2. Disallowed Concomitant Therapy

Concomitant treatment with any of the following is not allowed while receiving study treatment, unless approved by the Medical Monitor:

- Any opioids.
- Any alternative drug treatments directed toward the treatment of MS such as long-term immunosuppressant therapy or other immunomodulatory treatments (including but not limited to IFN- β , IFN- α , GA, natalizumab, alemtuzumab, B-cell depleting agents, cyclophosphamide, methotrexate, azathioprine, mycophenolate mofetil, DMF, teriflunomide, 4-aminopyridine, S1P receptor modulators such as fingolimod, or related products).
- Any investigational product, including investigational symptomatic therapies for MS and investigational therapies for non-MS indications.
- Any systemic steroid therapy including, but not limited to, oral corticosteroids (e.g., prednisone) or periodic (e.g., monthly) treatment with IVMP. Systemic steroid therapy is permissible for the treatment of [REDACTED] as per local regulations and/or prescribing practice, for up to 5 days maximum duration. Refer to Section 7.2.2 for allowed use of treatments for [REDACTED]. Steroids that are administered by nonsystemic routes (e.g., topical, inhaled) are allowed.
- Any live or attenuated immunization or vaccination.
- Total lymphoid radiation, cladribine, T-cell or T-cell receptor vaccination, any therapeutic monoclonal antibody, mitoxantrone, cyclosporine, IV immunoglobulin, plasmapheresis, or cytapheresis.

CONFIDENTIAL

The information contained herein may not be used, disclosed, or published without the written consent of Biogen MA Inc.

If another MS treatment is initiated (or if DRF is restarted) before the lymphocyte count returns to LLN during the protocol-required ALC follow-up monitoring period, the participant must be discontinued from the study.

Participants who receive any of these restricted medications without approval from the Medical Monitor will be required to permanently discontinue study treatment and will be withdrawn from the study as described in Section 8.3. Participants who initiate a protocol-defined disallowed concomitant therapy must complete an ET Visit and withdraw from the study.

